The results reported in these papers will follow the strategy set out here. Subsequent analyses of a more exploratory nature will not be bound by this strategy, though they are expected to follow the broad principles laid down here. The principles are not intended to curtail exploratory analysis (e.g. to decide cut-points for categorisation of continuous variables), nor to prohibit accepted practices (e.g. transformation of data before analysis), but they are intended to establish rules that will be followed, as closely as possible, when analysing and reporting data.

Any deviations from this SAP will be described and justified in the final report or publication of the trial (using a table as shown in Appendix A). The analyses will be carried out by an appropriately qualified statistician, who should ensure the integrity of the data during the data cleaning processes.

2. Background and rationale

The background and rationale for the trial are outlined in detail in the protocol document (current version 6.0). In brief, the study aims to evaluate the implementation of early detection of Postpartum Haemorrhage (PPH) and the use of the WHO MOTIVE 'first response' PPH treatment bundle on clinical, implementation and resource use outcomes. This will be done using a cluster randomised trial design, randomising health facilities to either the E-MOTIVE intervention or to usual care after a baseline phase in which all facilities are subject to usual care.

3. Trial objectives

Primary Objective:

Evaluate the implementation of the E-MOTIVE intervention compared with usual care on clinical, implementation and resource use outcomes.

The secondary objectives are as follows:

1. Assess the cost-effectiveness of the E-MOTIVE intervention compared with usual care from a public healthcare system perspective.

2. Develop, optimise and manualise an implementation strategy, with parallel process evaluation alongside the trial, ready for scaling-up of the E-MOTIVE intervention if found to be effective.

The proposed methods for the secondary objectives will be detailed elsewhere.

4. Trial methods

4.1. Trial design

E-MOTIVE is a prospective, multi-country parallel cluster randomised trial with a baseline control phase (see Appendix B for a schematic of trial design), along with a mixed-methods pilot, process evaluation, and health economic evaluation.

Patients will be included from secondary-level health facilities across the included countries: Kenya, Nigeria, South Africa, and Tanzania.

The unit of analysis, a patient, is defined as a woman who has a verified vaginal birth in a study facility.

A woman with a verified vaginal birth is a woman for whom we have patient and birth information.

In E-MOTIVE, a cluster is defined as a secondary-level health facility. Throughout the rest of this document, the term cluster will be used to represent this.

4.2. Trial interventions

Intervention: The E-MOTIVE intervention targets healthcare providers and consists of an implementation strategy for early detection of PPH, which allows the initiation of the 'first response' treatment bundle, which is called MOTIVE, consisting of uterine Massage, Oxytocic drugs, Tranexamic acid, IV fluids and Examination & Escalation (See Protocol, Box 2). The timing, dosing and manner with which these interventions will be implemented will be in line with WHO recommendations and local protocols where available. The implementation strategy focuses on (i) calibrated drape with trigger line, (ii) E-MOTIVE emergency trolley and/or carry case, (iii) simulation-based training on-site with peer-assisted learning, (iv) feedback of actionable data to providers, and (v) local E-MOTIVE champions.

Control: Usual care with dissemination of the current guidelines. In usual care, 'first response' treatment may include some or all of the components of the MOTIVE treatment

bundle. All components are routinely available in all facilities and recommended for all women with PPH, but currently are used inconsistently by healthcare providers.

4.3. Randomisation

After regulatory approvals, 78 clusters from Kenya, Nigeria, South Africa and Tanzania will enter a 7-month baseline period in which they will be following usual care with dissemination of the current guidelines. After this 7-month baseline period, we will allocate 78 clusters (a 1:1 ratio) to either the E-MOTIVE intervention or usual care for 7 months, with an allowance of two months ('transition phase') for full implementation and embedding of the intervention. Clusters not allocated to E-MOTIVE will continue to follow usual care as per the baseline period for the remainder of the intervention phase.

The recruitment of all clusters will be completed within a 3-month period. Following the baseline period, randomisation will be implemented using a minimisation algorithm to ensure a balance of the intervention and control facilities for the following (measured at the cluster-level during the first 5 months of the baseline phase):

1. Number of vaginal births
2. Proportion of births with the composite primary outcome (before randomisation)
3. Oxytocin quality
4. Number of intervention and control clusters in each country

Details of how these are calculated are presented below. The minimisation will be stratified in each country (separate minimisations) to increase the balance in all of the above covariates within a country.

Number of vaginal births

After the first five months of the baseline phase has completed, for each cluster, we will gather the total number of births and the number of months of data collection to calculate the cluster's monthly birth rate. We will then use the cluster's monthly birth rate to determine the country's median birth rate. The clusters above and below the country median will form the categories for the minimisation algorithm.

The proportion of births with the composite primary outcome before randomisation

After the first five months of the baseline phase has completed, for each cluster, we will gather the total number of births and the total number of events. The ratio of the number of events to the number of births will give us the proportion of births with the composite outcome for that cluster. We will then use the cluster's primary outcome proportion to determine the country's median primary outcome proportion. The clusters above and below the country median will form the categories for the minimisation algorithm.

Oxytocin Quality

The quality of oxytocin (measured during the baseline phase) will be dichotomised as $\leq 90\%$ and $>90\%$ to form the categories for the minimisation algorithm.

Number of intervention and control clusters in each country

In an attempt to balance the number of clusters allocated to each arm, we will include a covariate that represents the number of clusters assigned to treatment and control, as there is evidence that this improves balance in the number of clusters in each arm [1].

Minimisation implementation

The randomisation of health facilities will be performed using a validated minimisation algorithm that follows the Pocock and Simon range method[2] using the "rct_minim" command in Stata 16. The first cluster in each country will be allocated completely at random. All further clusters will be allocated using the minimisation algorithm. To reduce the predictability of allocation and to ensure a balance in covariates across arms, a small random element (10%) will be included in the algorithm. A random element is typically included to better protect the blinding of treatment allocations when recruiting new facilities. A random element of 10% would mean we expect 90% of clusters to be allocated using the minimisation algorithm to the arm that minimises covariate imbalance, and 10% are not.

The randomisation of health facilities will be performed using a validated minimisation algorithm and implemented by an independent statistician from the University of Birmingham Clinical Trials Unit (BCTU). Full details of the randomisation specification will be stored in a confidential document at the University of Birmingham Clinical Trials Unit (BCTU).

4.4. Timing of outcome assessments

All outcomes are measured between birth and discharge from the cluster or higher-level facility (if transferred).

4.5. Primary outcome measure

The primary outcome is a composite of the following three clinical outcomes:

- Primary severe PPH (defined as blood loss ≥ 1000 ml) following vaginal birth in the cluster measured up to 2 hours postpartum.
- Postpartum laparotomy for bleeding until discharge from the cluster.
- Postpartum maternal death from bleeding until discharge from the cluster.

If any of the components occur, this will be deemed as positive for the primary outcome.

The components of the composite primary outcome will be treated as secondary outcomes and examined individually as is recommended [3].

Measurement of blood loss

Blood loss will be collected using blood collection drapes for all women after vaginal birth. All facilities will use non-calibrated drapes during the baseline phase. During the intervention phase, clusters allocated to the control arm will continue to use non-calibrated drapes and clusters allocated to the intervention arm will use calibrated drapes containing measurement and trigger lines. The calibrated drapes are identical to the non-calibrated drapes with the only difference of having measurement and trigger lines to aid healthcare providers detect and treat PPH early. Blood loss will be measured for all women by weighing the blood collection drapes at the first hour postpartum, or if the bleeding continues, the blood collection will be extended to the second hour postpartum. The weight of the blood collection drape containing the blood will be recorded using digital weighing scales. If there is excessive, additional blood loss beyond the second hour postpartum up to 24 hours postpartum a visual estimation of blood loss will also be provided, and this will be included in the overall blood loss measurement as a secondary clinical outcome.

Only blood loss data that has been source verified will be included in the primary analysis – see below for details. Blood loss data that has not been source verified is included in a sensitivity analysis.

Source-verified data

Analyses of outcomes with blood loss data will only include blood loss that has been source-verified. Blood loss measured using the blood collection drape, which is source-verified will have a corresponding photograph, which is uploaded to a secure portal, of the drape on the E-MOTIVE digital weighing scale displaying the drape weight. The photograph should also display the drape weight documented on the E-MOTIVE stickers before being placed in the patient notes. The drape weight value entered on to the E-MOTIVE REDCap database is verified against the drape weight in the photograph and the photograph is linked to the patient record on the database using the E-MOTIVE patient I.D number.

Blinded Endpoint Review Committee

A Blinded Endpoint Review Committee (BERC) will assess incoming data relevant to the primary outcome to confirm if any postpartum laparotomy was performed for bleeding and if any maternal death was due to bleeding. Initially, two central independent reviewers (identified by the TMG) will review de-identified data via the online E-MOTIVE database where there is a case of postpartum laparotomy and/or maternal death. The reviewers will not be able to view the facility's responses as to whether the postpartum laparotomy was for bleeding and/or the maternal death was due to bleeding. Each reviewer will be prompted to log in to the E-MOTIVE database and record their assessment on an electronic case report form (e-CRF) following receipt of an automated notification. If there is discordance between the assessments of the two reviewers or if their assessment conflicts with the assessment provided by the facility then a further assessment will be required by a central independent arbitration committee of five members convened by the TMG. The committee will meet as frequently as required and a decision will be made by a majority vote. The arbitration

committee will have access to the facility assessment (on the Discharge Outcome form) and the two independent reviewer assessments in order to make their decision. The Programme Manager (or delegate) will minute committee discussions and enter a summary of the discussions along with their decision on to the e-CRF. The review by the BERC members will be undertaken blinded to the randomised allocation of the health facility. Members of the BERC are required to formally register their assent to join the committee by signing a separate charter. Further details of the BERC can be found in their charter.

4.6. Secondary clinical and implementation outcome measures

Key Implementation Outcomes

The key implementation outcomes are:

- 1) Postpartum haemorrhage detection
- 2) Compliance with the MOTIVE bundle

These are defined below.

Postpartum haemorrhage detection

Postpartum haemorrhage (PPH) detection has the following numerator and denominator: women who objectively had PPH (source verified blood loss ≥ 500 mL after weighing the drape) and were diagnosed with PPH by the birth attendants divided by the total number of women who objectively had PPH (source verified blood loss ≥ 500 mL after weighing the drape).

Compliance with the MOTIVE bundle

Compliance with the MOTIVE bundle has the following numerator and denominator: women who objectively had PPH and were treated with the PPH bundle following a diagnosis of PPH by the birth attendants divided by the total number of women who objectively had PPH (blood loss ≥ 500 mL after weighing of the drape). Compliance with the MOTIVE bundle is defined as adherence to the three core elements of the bundle: administration of oxytocic drugs, TXA and IV fluids. If all three core elements are administered when a PPH is diagnosed, this will be deemed positive for bundle compliance. If any of the three core elements are not administered when a PPH is diagnosed, then this will be deemed negative for bundle compliance.

Secondary Clinical Outcomes

The secondary clinical outcomes are based on the Core Outcome Set for PPH treatment, and are the following:

1. Laparotomy postpartum until discharge from the cluster*;
2. Laparotomy with compression sutures postpartum until discharge from the cluster*;
3. Laparotomy with arterial ligation postpartum until discharge from the cluster*;
4. Hysterectomy postpartum until discharge from the cluster*;
5. Hysterectomy postpartum for bleeding until discharge from the cluster*;
6. All-cause maternal mortality postpartum until discharge from the cluster*;
7. Blood loss (reported in ml) up to 24 hours postpartum†;

8. Primary PPH defined as blood loss ≥ 500 ml up to 24 hours postpartum[†];
9. Duration of hospitalisation postpartum;
10. Duration of ICU hospitalisation postpartum until discharge from the cluster[†];
11. Transfers to higher-level facility postpartum until discharge from the cluster;
12. All-cause neonatal mortality postpartum until discharge from the cluster*;
13. Use of Non-pneumatic anti-shock garment (NASG) postpartum[†];
14. Use of uterine balloon tamponade postpartum until discharge from the cluster[†];
15. Blood transfusion postpartum until discharge from the cluster^{†*};
16. Blood transfusion for postpartum haemorrhage until discharge from the cluster^{†*};
17. Intensive Care Unit (ICU) admissions postpartum until discharge from the cluster^{†*};
18. Primary severe PPH (defined as blood loss ≥ 1000 ml) following vaginal birth in the cluster measured up to 2 hours postpartum[†];
19. Postpartum laparotomy for bleeding until discharge from the cluster*;
20. Postpartum maternal death from bleeding until discharge from the cluster*;

[†]Combined clinical and quality of care exploratory outcomes where we may observe an increase or a reduction if E-MOTIVE is effective.

*In cases where a woman is transferred to another facility postpartum, discharge from the cluster relates to the facility the woman is transferred to and the relevant outcomes will be obtained from the facility to which the woman was referred.

Secondary Implementation Outcomes

The secondary implementation outcomes are:

1. PPH treatment (with the following numerator and denominator: women diagnosed with PPH by the birth attendants divided by the total of women having a vaginal birth in the health facility);
2. Bundle usage (with the following numerator and denominator: women treated with the PPH bundle following a diagnosis of PPH by the birth attendants divided by the total of women having a vaginal birth in the health facility);
3. Bundle usage for PPH (with the following numerator and denominator: women treated with the PPH bundle following a diagnosis of PPH by the birth attendant divided by the total of women diagnosed with PPH by the birth attendants);
4. Uterine massage;
5. Oxytocin use;
6. Misoprostol use;
7. TXA use;
8. Intravenous fluids use;
9. Examination of the genital tract;
10. Number of women receiving any treatment uterotonic;
11. Number of women requiring additional treatment interventions (not responding to the MOTIVE bundle).

All secondary implementation outcomes will be reported with three denominators:

- The total study population.
- Women diagnosed with PPH by the birth attendant.
- Women who objectively had PPH (blood loss \geq 500 mL after weighing the drape).

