6. OUTCOME MEASURES AND STUDY PROCEDURES

6.1. Primary outcome

The primary outcome is a composite of the following three clinical outcomes: 1) primary severe PPH defined as blood loss ≥ 1000 ml following a vaginal birth in the facility measured up to 2 hours postpartum; 2) postpartum laparotomy for bleeding until discharge from the health facility*; and 3) postpartum maternal death from bleeding until discharge from the health facility*. If any of the components occur, this will be deemed as positive for the primary outcome.

Measurement of blood loss

Blood loss will be collected using blood collection drapes for all women after vaginal birth. All facilities will use non-calibrated drapes during the baseline phase. During the intervention phase, facilities allocated to the control arm will continue to use non-calibrated drapes and facilities allocated to the intervention arm will use calibrated drapes containing measurement and trigger lines. The calibrated drapes are identical to the non-calibrated drapes with the only difference of having measurement and trigger lines to aid healthcare providers detect and treat PPH early. Blood loss will be measured for all women by weighing the blood collection drapes at the first hour postpartum or if bleeding continues, the blood collection will be extended to the second hour postpartum. The weight of the blood collection drape containing the blood will be recorded using digital weighing scales. If there is excessive, additional blood loss beyond the second hour postpartum up to 24 hours postpartum a visual estimation of blood loss will also be provided, and this will be included in the overall blood loss measurement as a secondary clinical outcome.

Only blood loss data that has been source verified will be included in the primary analysis – see section 11.2 for details. Blood loss data that has not been source verified is included in a sensitivity analysis.

Blinded Endpoint Review Committee

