The key secondary implementation outcomes of special interest are 1) PPH detection (with the following numerator and denominator: women who objectively had PPH (source-verified blood loss ≥ 500 mL after weighing the drape) and were diagnosed with PPH by the birth attendants divided by the total number of women who objectively had PPH (source verified blood loss ≥ 500 mL after weighing the drape), and 2) compliance with MOTIVE bundle (with the following numerator and denominator: women who objectively had PPH and were treated with the PPH bundle following a diagnosis of PPH by the birth attendants divided by the total number of women who objectively had PPH (blood loss ≥ 500 mL after weighing of the drape). Compliance with the MOTIVE bundle is defined as adherence to three core elements of the bundle: administration of oxytocic drugs, TXA and IV fluids. If all three core elements are administered when a PPH is diagnosed, this will be deemed positive for bundle compliance. If any of the three core elements are not administered when a PPH is diagnosed, then this will be deemed negative for bundle compliance. It is hypothesised that the causal mechanism underpinning the intervention is that it will increase the rate at which PPH is diagnosed; and that an increase in awareness of women suffering from PPH will subsequently lead to an increase in uptake in the interventions to stop PPH from progressing to severe consequences. This will ultimately lead to a reduction in the proportion of women suffering adverse outcomes from PPH.

Other implementation outcomes are:

1. PPH treatment (with the following numerator and denominator: women diagnosed with PPH by the birth attendants divided by the total of women having a vaginal birth in the health facility)
2. Bundle usage (with the following numerator and denominator: women treated with the PPH bundle following a diagnosis of PPH by the birth attendants divided by the total of women having a vaginal birth in the health facility)
3. Bundle usage for PPH (with the following numerator and denominator: women treated with the PPH bundle following a diagnosis of PPH by the birth attendant divided by the total of women diagnosed with PPH by the birth attendants);
4. Uterine massage;
5. Oxytocin use;
6. Misoprostol use;
7. TXA use;
8. Intravenous fluids use;
9. Examination of the genital tract;
10. Number of women receiving any treatment uterotonic;

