11. Number of women requiring additional treatment interventions (not responding to the MOTIVE bundle).

All secondary implementation outcomes will be reported with three denominators: the total study population; women diagnosed with PPH by the birth; and women who objectively had PPH (blood loss ≥ 500 mL after weighing the drape) unless otherwise specified.

The data are routinely collected as part of normal clinical practice and women will not be approached for additional trial-specific data or follow up at any point.

From each participating health facility, we will extract the following additional outcomes weekly:

1. Vaginal births (number);
2. Caesarean sections (number);

From each participating health facility, we will extract the following additional outcomes monthly:

3. Availability of bundle components;
4. Availability of NASG;
5. Availability of UBT;
6. Availability of blood transfusion;
7. Availability of surgical theatre for obstetrics;
8. Availability of ICU;
9. Availability of skilled birth attendants.

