7.3. Summary Measures

For all binary outcomes – this includes the primary composite outcome, the key secondary implementation outcomes, and other secondary clinical and implementation outcomes, we will summarise the number of patients who experience the outcome, and the percentage of the group this corresponds to. Summary statistics will be presented stratified by trial arm (E-MOTIVE or control) and time-period (baseline phase or post-randomisation phase). To quantify the effect of E-MOTIVE, the intervention effect will be presented using relative risk and risk differences – as per CONSORT recommendations³.

For secondary outcomes that are continuous, we will summarise using means and standard deviations or medians and inter-quartile ranges as appropriate. Histograms will be produced to determine which summary statistic is most appropriate. We will present summary statistics stratified by trial arm (E-MOTIVE or control) and time-period (baseline phase or post-randomisation phase). To quantify the effect of E-MOTIVE, the intervention effect will be presented using the mean difference (difference in means between E-MOTIVE and usual care).

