Appendix E5: Secondary outcomes results

Table 4: Main outcomes. Values are number (percentage) unless otherwise stated.

Outcomes	E-MOTIVE		Control		Risk Ratio ¹ (95% CI)	Risk Difference ¹ (95% CI)*
	Baseline period (N =)	Post-randomisation period (N =)	Baseline period (N =)	Post-randomisation period (N =)		
Secondary Clinical Outcomes						
Severe PPH ²						
Laparotomy for bleeding						
Maternal mortality from bleeding						
Primary PPH ³						
Laparotomy						
Laparotomy with compression sutures						
Laparotomy with arterial ligation						
Hysterectomy						
Hysterectomy for bleeding						
All cause maternal mortality						
All cause neonatal mortality						
Non-pneumatic anti-shock garment (NASG)						
Uterine balloon tamponade						
Blood transfusion						
Blood transfusion for bleeding						
ICU admissions						
Transfer to higher level facility						

	E-MOTIVE				Control		Mean difference ¹ (95% CI)*	
	Baseline period (N =)	Post-randomisation period (N =)	Baseline period (N =)	Post-randomisation period (N =)				
Blood loss 2 hours postpartum (ml), mean (SD)						-		
Blood loss 24 hours postpartum (ml), mean (SD)						-		
Duration of hospitalisation (hours), mean (SD)						-		
Duration of ICU hospitalisation (hours), mean (SD)						-		
Other Secondary Implementation Outcomes	E-MOTIVE		Control		Risk Ratio ¹ (95% CI)		Risk Difference ¹ (95% CI)*	
In women with ≥500ml blood loss	Baseline period (N =)	Post-randomisation period (N =)	Baseline period (N =)	Post-randomisation period (N =)				
Uterine massage								
Oxytocin use								
Misoprostol use								
Tranexamic acid use								
Intravenous fluids use								
Examination of the genital tract								
Women receiving any treatment uterotonic								
Women requiring additional treatment interventions								
In women diagnosed with PPH by HCP⁴								
Bundle compliance ⁵								
Uterine massage								
Oxytocin use								

Misoprostol use
 
Tranexamic acid use
 
Intravenous fluids use
 
Examination of the genital tract
 
Women receiving any treatment uterotonic
 
Women requiring additional treatment interventions
 
In all women
 
Detection of PPH by HCP ⁴
 
Bundle compliance ⁵
 
Uterine massage
 
Oxytocin use
 
Misoprostol use
 
Tranexamic acid use
 
Intravenous fluids use
 
Examination of the genital tract
 
Women receiving any treatment uterotonic
 
Women requiring additional treatment interventions
		

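### Risk ratios and risk differences are planned among women diagnosed with PPH by the attendant, a post-randomisation group that E-MOTIVE is designed to enlarge; that block should be descriptive only

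*SAP*

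**What the plan says.** SAP 4.6 says that "All secondary implementation outcomes will be reported with three denominators": the whole study population, "Women diagnosed with PPH by the birth attendant", and women with a weighed loss of at least 500 mL. Protocol 6.2 has the same three, unless otherwise specified. One outcome, *Bundle usage for PPH*, has the second denominator by definition: bundle-treated women "divided by the total of women diagnosed with PPH by the birth attendants".

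SAP 7.3 covers all binary outcomes, implementation outcomes included, and states that "the intervention effect will be presented using relative risk and risk differences". The Table E5 shell follows this. Its block headed "In women diagnosed with PPH by HCP" sits under risk ratio and risk difference columns and has rows for bundle compliance, the individual components, any treatment uterotonic, and additional treatment interventions.

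On mechanism, Protocol 6.2 hypothesises that "it will increase the rate at which PPH is diagnosed". Protocol 6.1 adds that after randomisation "facilities allocated to the intervention arm will use calibrated drapes containing measurement and trigger lines", while control facilities keep the non-calibrated drape.

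SAP 5.1 and 5.2 call for caution with secondary results and give multiplicity as the reason. Protocol 11.2 asks for caution without giving a reason.

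**The concern.** Whether a woman enters this denominator is decided by the attendant after randomisation, using a detection tool that differs by arm. If control staff mainly recognise the heavier bleeds and E-MOTIVE staff also recognise the moderate ones, the E-MOTIVE denominator has a milder case mix. A between-arm ratio then mixes any effect of the intervention with that shift.

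The planned analysis does not remove it. The constrained baseline model (SAP 7.4.2, 7.5) adjusts for period and cluster-level factors, with no term for blood loss. The case-mix change occurs exactly where the exposure indicator equals 1, so it loads onto the treatment coefficient. The sensitivity analyses in SAP 7.11 are limited to the primary and key implementation outcomes. Appendix E9 labels some columns as target population but gives a single patient population, all women with a verified vaginal birth, so no estimand exists for the diagnosed subset.

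The row most open to misreading is additional treatment, which SAP 4.6 glosses as non-response to the bundle. A ratio below 1 with a confidence interval would be read as fewer treatment failures. A caution about multiplicity warns of chance findings, not of systematic non-comparability.

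**Working it through.** The plan states no expected size for these comparisons, so there is no figure to reproduce. The check asks what ratio appears among diagnosed women when the probability of the outcome is the same in both arms within each severity stratum and only detection differs.

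**Inputs**
- Overall detection of objective PPH: 50% control, 90% E-MOTIVE. These are the planning values for the Pakistan before-and-after study (Protocol Appendix A), used here as an assumption; they are not figures for the four-country trial.
- Share of objective PPH that is severe (at least 1000 mL): 20% to 40%, assumed.
- Control detection of severe PPH: 60% to 90%, assumed. Detection of moderate PPH (500 to 999 mL) is then set so that the overall figure is 50%. E-MOTIVE detection: 90% in both strata.
- Bundle use once diagnosed: 235/886 = 26.5% moderate, 68/96 = 70.8% severe. These are treatment-uterotonic figures at 500–600 mL and 1000–1100 mL from the cited multi-country carbetocin trial (Protocol 1.1), borrowed as a stand-in.
- Additional treatment: 5% moderate, 25% severe, assumed, in both arms.

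**Formula.** With severity share w, detection d and outcome probability p in each stratum:

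P(outcome | diagnosed) = Σ(w·d·p) / Σ(w·d)

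**One case in full** (30% severe; control detection of severe 80%)
- Control detection of moderate = (0.50 − 0.30×0.80)/0.70 = 0.37.
- Additional treatment, control: (0.24×0.25 + 0.26×0.05)/0.50 = 14.6%. E-MOTIVE: 0.30×0.25 + 0.70×0.05 = 11.0%. RR = 0.75, RD = −3.6 points.
- Bundle use, control: (0.24×0.708 + 0.26×0.265)/0.50 = 47.8%. E-MOTIVE: 0.30×0.708 + 0.70×0.265 = 39.8%. RR = 0.83, RD = −8.0 points.

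**Range**

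| Severe share | Control detection, severe / moderate | Additional treatment RR (RD, points) | Bundle use RR (RD, points) |
|---|---|---|---|
| 20% | 60% / 47.5% | 0.92 (−0.8) | 0.95 (−1.8) |
| 30% | 80% / 37% | 0.75 (−3.6) | 0.83 (−8.0) |
| 40% | 90% / 23% | 0.67 (−6.4) | 0.76 (−14.2) |

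The first and last rows are the ends of the whole grid.

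**Limits.** For additional treatment the spurious ratio can be written (0.50/0.90) × (s1/s0), where s1 and s0 are the shares of women needing additional treatment who are diagnosed under E-MOTIVE and control.
- s1 = s0 = 1: 0.56, the extreme.
- s0 = 0.7, s1 = 0.9: 0.71.
- Detection unrelated to severity (s0 = 0.5, s1 = 0.9): 1.00.

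The ratio is also 1.00 if the outcome does not depend on severity.

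**Simulation.** There were 500 null runs with 39 clusters per arm, comparing cluster proportions after randomisation by t-test; this is not the SAP's model. PPH was set at 10% of births, and the middle row's detection and additional-treatment assumptions were used. Among diagnosed women the mean RR was 0.76, with p<0.05 in 91% of runs. Among all women with objective PPH it was 1.01. The second result holds by construction, because the simulation does not let E-MOTIVE change who reaches 500 mL.

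**The case against.** Several points on the other side are sound. The same rows are also reported for all women and for women with objective PPH, so a denominator artefact could be spotted. No p-values are planned here by default, and results are labelled supporting evidence only. Care given once PPH is recognised is a legitimate fidelity measure (Protocol 6.3), so the percentages are worth having. None of this makes the effect estimate interpretable, but it does confine the problem to secondary results.

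Four stronger readings are tempting, and the documents do not support them.
- **That the bias is automatic.** It needs detection to favour severe bleeds more in control than in E-MOTIVE, and the outcome to depend on severity. The uterotonic gradient in Protocol 1.1 supports a link between treatment and severity. It counts all women in each blood-loss band, though, so part of it may reflect recognition rather than treatment after diagnosis.
- **That a ratio of 0.56 should be expected.** That requires every woman needing additional treatment to be diagnosed in both arms. In the same cited data about 30% of women at 1000–1100 mL received no treatment uterotonic, so complete recognition cannot be taken for granted.
- **That every row would flatter E-MOTIVE.** For bundle and component use, a milder case mix lowers the E-MOTIVE percentage, so the artefact runs against the intervention.
- **That the objective-PPH denominator is clean.** It is also measured after randomisation, and SAP 4.6 marks primary PPH as an outcome that may rise or fall if E-MOTIVE works. Only the all-women denominator keeps the randomised comparison.

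**Conclusion.** The point holds as a conditional one. The plan would publish risk ratios and risk differences, with confidence intervals, in a subgroup defined by a post-randomisation decision that the intervention is meant to change. No severity covariate, estimand, sensitivity analysis or stated caution addresses this.

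The sizes, 0.67 to 0.92 for additional treatment and 0.76 to 0.95 for bundle use with no true effect within severity, are illustrations. They rest on the borrowed 50% and 90% detection values, the assumed severity mix and control detection gradient, and the assumed or borrowed outcome probabilities. They show that the artefact can be as large as an effect that readers would take seriously; they do not predict this trial's figures. Over-diagnosis below 500 mL in the E-MOTIVE arm, not modelled, would dilute that arm further.

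A reader might infer that the trial's main conclusion is in doubt. It is not on this ground: the primary outcome is defined in all women, and PPH detection and bundle compliance, the two key implementation outcomes, use the objective-PPH denominator.

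**What to change.** 1. In Table E5, show the diagnosed-women block, including *Bundle usage for PPH*, as counts and percentages by arm and period, labelled as a description of fidelity. Remove its risk ratio and risk difference columns.
2. Amend SAP 4.6 and 7.3 to match, stating that this block conditions on a diagnosis made after randomisation.
3. State that the all-women risk ratio and risk difference are the randomised comparison for secondary implementation outcomes.
4. Keep the objective-PPH risk ratio and risk difference, with a footnote that this denominator is also measured after randomisation and may itself be changed by E-MOTIVE.
5. Define target population in Appendix E9 for each column that uses the term.

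These are text and table edits that need no new data; if the tables have already been produced, the change can be recorded in the deviations table of SAP Appendix A. The cost is the loss of cluster-adjusted effect estimates and their intervals for the diagnosed block. Readers can still divide the displayed percentages, so the label in item 1 and the statement in item 2 matter as much as the removed columns.
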